5.1.3. Reactogenicity/Safety

- For a given participant and the analysis of solicited events within 4 days postvaccination, missing or non-evaluable measurements will not be replaced. Therefore, the analysis of solicited events will include only vaccinated participants with documented solicited safety data (i.e., paper diary completed).
- For analysis of unsolicited AEs, serious adverse events (SAEs), potential immunemediated diseases (pIMDs) and concomitant medications, all vaccinated participants will be considered. Participants who did not report an event or concomitant medication will be considered as participants without the event or the concomitant medication, respectively.

5.2. Analysis of demography and baseline characteristics

5.2.1. Analysis planned in the protocol

Descriptive summaries will be performed for each group (RSV_annual, RSV_flexible revaccination and RSV_1dose) and overall. The same will be performed in each subset (humoral immune subset and CMI subset).

Demographic/baseline characteristics (age at vaccination in years, sex, race, ethnicity, type of residence (CD/LTCF) and smoking status) will be summarized using descriptive statistics:

- Frequency tables will be generated for categorical variables such as race.
- Mean, median, standard deviation and range will be provided for continuous data such as age.

The distribution of participants will be tabulated as a whole and per group, for each age category, and for each subset.

The number of doses of the study intervention administered will be tabulated by group and by visit.

Withdrawal status will be summarized by group using descriptive statistics:

- The number of participants enrolled into the study as well as the number of participants excluded from Per Protocol (PP) analyses will be tabulated.
- The numbers of participants withdrawn from the study will be tabulated according to the reason for withdrawal.

Participant disposition in the ES and PPS will be reported as a whole and per group

The number and percentage of participants using concomitant medication (any medication, any antipyretic and any antipyretic taken prophylactically, respectively) during the 4-day follow-up period (i.e., on the day of vaccination and 3 subsequent days) and during the 30-day follow-up period (i.e., on the day of vaccination and 29 subsequent days) will be summarized by group after each vaccine dose and after the revaccination.

5.2.2. Additional considerations

- The analysis of demographic characteristics by group will be performed on the ES and on the PPS.
- Demography and baseline characteristics will also be summarized by sex and region.
- A summary of important protocol deviations leading to elimination from any analyses will be provided by group, based on the Enrolled Set.
- Medical history will be tabulated by System Organ Class (SOC), High Level Term (HLT) and Preferred Term (PT).

5.3. **Primary endpoint(s)**

5.3.1. Analysis planned in the protocol

The primary analysis for immunogenicity will be performed on the PPS. If the percentage of vaccinated participants with serological results excluded from the PPS for immunogenicity is at least 5% for at least 1 visit and at least 1 group, a second analysis will be performed on the ES.

5.3.1.1. Humoral immune response – up to Month 12

The analysis of the primary vaccination timepoints up to Month 12 will be performed for each group and for the 3 groups pooled. For each timepoint with blood sample collection for humoral immune response up to Month 12 and for each assay (RSV-A/-B neutralization assays), unless otherwise specified, the following analyses will be performed:

Within groups evaluation:

- Percentage of participants with antibody titers/concentrations above or equal to the technical assay cut-off and their exact 95% confidence interval (CI) will be tabulated.
- GMTs/GMCs and their 95% CI will be tabulated and represented graphically. Furthermore, to account for all the timepoints at which the blood samples are collected, a mixed effects model (see Section 5.4.3.1) will be fitted, from which the GMTs/GMCs will be computed.
- Antibody titers/concentrations will be displayed using reverse cumulative curves.
- The MGI i.e. geometric mean of ratios of antibody titer/concentrations will be tabulated with 95% CI.

5.4. Secondary endpoint(s)

5.4.1. Humoral immune response

The same analyses as described above for the primary endpoint will be performed for RSVPreF3-specific IgG ELISA up to Month 12 and for each timepoint with blood sample collection for humoral immune response **from study Month 13 up to study end** and for each assay (RSVpreF3-specific IgG **ELISA and RSV-A/-B neutralization assays**). For Month 13, Month 18, and Month 24, the analyses will be tabulated for RSV_annual group versus the pooled RSV_flexible revaccination and RSV_1dose groups. From Month 25 up to study end, the analyses will be performed by group.

Only the analyses requiring further clarification of the exact timepoints analyzed are summarized below:

Within groups evaluation:

- The MGI i.e. geometric mean of ratios of antibody titer/concentrations will be tabulated with 95% CI:
 - For each post-primary vaccination time point (at Months 18, 24, 30 and 36 when applicable) over pre-primary vaccination (Day 1),
 - For each post-revaccination time point over corresponding pre-revaccination (Months 12 and 24) in the RSV_annual group,
 - For each post-revaccination timepoint over corresponding pre-revaccination (Month 24) in the RSV_flexible revaccination group,
 - For 1 month post-revaccination at Month 12 (Month 13) over 1 month post-Dose 1 vaccination (Day 31) in RSV_annual group.
 - For 1 month post-revaccination at Month 24 (Month 25) over 1 month post-revaccination at Month 12 (Month 13) in RSV_annual group
 - For 1 month post-revaccination at Month 24 (Month 25) over 1 month post-Dose 1 vaccination (Day 31) in RSV_flexible revaccination group.

In addition, the following evaluation will be performed:

• The kinetics of GMTs/GMCs will be plotted as a function of time for participants with results available at all post vaccination timepoints.

The immunogenicity analysis will be performed overall, by sex, age category (age at Dose $1: \ge 65$ YOA, ≥ 70 YOA, ≥ 80 YOA, 60-69 YOA and 70-79 YOA), and region (North America, Europe, Asia).

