4.2. Scientific rationale for study design (Amended: 01 April 2022)

There is uncertainty about the persistence of the immune response to the RSVPreF3 OA investigational vaccine administered as a single dose and the level of immune response that may be required for protection. In addition, older adults may require repeated dosing to maintain protection against the RSV disease over several seasons. The study RSV OA=ADJ-004 has been designed to consider the possibility of a decline in the immune response through the assessment of persistence over 3 years, while also evaluating revaccination as early as the second year to generate data, should an annual revaccination be required.

For that reason, the study is designed not only to evaluate the safety, the reactogenicity, the immunogenicity profile and the long-term persistence of the immune response up to 3 years following a single dose vaccination regimen of the RSVPreF3 OA investigational vaccine in adults ≥60 YOA, but also to evaluate the immunogenicity, safety and reactogenicity of an additional vaccine dose through different revaccination schedules (annual revaccination or revaccination at a later stage):

- RSV_annual group will receive the first dose (Dose 1) at Day 1, followed by revaccination doses at 12 months post-Dose 1 and at 24 months post-Dose 1.
- RSV_flexible revaccination group will receive the first dose (Dose 1) at Day 1. A revaccination dose will be given 24 months post-Dose 1. Immunogenicity data from other studies using the same study intervention showed that following a two-dose vaccination schedule (0-2-month schedule), the immune response gradually declines over time but remains above baseline value up to 18 months post-Dose 2 and that a re-vaccination at 18 months post-Dose 2 (i.e., 20 months post-Dose 1) induced humoral and cellular immune responses.
- RSV_1dose group will receive a single dose (Dose 1) at Day 1.

The study will include the target population of older adults \geq 60 YOA living in the community (community dwelling [CD]) or living in a LTCF and presenting with medically stable condition.

The vaccine formulation was selected in a previous study, where the vaccine was administered intramuscularly according to a 0, 2-month vaccination schedule. Please refer to the IB for details.

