9.2. Sample size determination (Amended: 01 April 2022)

This study is planned to enroll ~1650 participants randomized according to 3:1:1 ratio to 1 of the 3 study groups: RSV_annual, RSV_flexible revaccination, and RSV_1dose respectively.

The proposed sample size is based on the following considerations:

• Ensure a sufficient number of participants to evaluate with adequate precision the immunogenicity after a single dose regimen up to 12 months post-vaccination (based on the 3 pooled RSV_annual, RSV_flexible revaccination and RSV_ldose groups) but also the immunogenicity after revaccination (based on RSV_annual and RSV_flexible revaccination groups).

- Ensure adequate description of the antibody kinetics after a single dose keeping the flexibility to give a revaccination to a part of the participants.
- Ensure an adequate sample size for evaluation of reactogenicity and safety profile following revaccination.

Approximately 345 participants will be enrolled in the humoral subset in the RSV_annual group and approximately 330 participants per group in the RSV_flexible revaccination and RSV_1dose groups. Approximately 345, 115 and 115 participants will be enrolled in the CMI subset in the RSV_annual, RSV_flexible revaccination, and RSV_1dose groups, respectively. A total of 990 and 330 participants will be enrolled in the RSV_annual and RSV_flexible revaccination groups, respectively, for evaluation of reactogenicity and safety profile following revaccination. A 20% rate of non-evaluable participants every year will be considered.

Withdrawals will not be replaced.

9.2.1. Evaluation of humoral immune response up to Month 12 (primary objective and first secondary objective)

At Month 12, the effect of a 1-dose primary schedule will be evaluated in terms of RSV-A/B neutralizing antibody titers and RSVPreF3-specific IgG concentrations. Approximately 804 participants in the (RSV_annual, RSV_flexible revaccination, and RSV_1dose) pooled group receiving a single dose of RSVPreF3 OA investigational vaccine will be evaluable for the humoral immune response at Month 12.

Table 17 shows the precision that can be obtained based on different values of standard deviations in terms of RSV-A/B neutralizing antibody titers, and RSVPreF3-specific IgG antibody concentrations.

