Study Groups	Number of participants	Age	Primary vaccination	Revaccination Year 1 (Month 12)	Revaccination Year 2 (Month 24)	Open
RSV_annual*	~990	≥60 years	RSVPreF3 OA investigational vaccine	RSVPreF3 OA investigational vaccine	RSVPreF3 OA investigational vaccine	х
RSV_flexible revaccination	~330	≥60 years	RSVPreF3 OA investigational vaccine	(none)	RSVPreF3 OA investigational vaccine	х
RSV_1dose	~330	≥60 years	RSVPreF3 OA investigational vaccine	(none)	(none)	х

* RSV_annual group will be split in 3 technical groups in SBIR in order to have a randomization ratio of 1:1:1:1:1: for treatment allocation and avoid predictability.

• **Groups and sub-groups definition for analysis:** Refer to the tables below for a description of the groups and subgroups labels that will be used in the Tables Figures and Listings (TFLs).

The analyses pertaining to timepoints up to Month 12 will be performed for each group and for the 3 groups pooled. From Month 13 up to study end, the analyses will be performed by group.

The following group names will be used in the TFLs:

Table 2 Group names and definition for footnote in the TFLs

Group order in tables	Group label in tables	Group definition for footnote	
1	RSV_annual	Participants receiving the first dose (Dose 1) of RSVPreF3 OA investigational vaccine at Day 1, followed by a revaccination dose at 12 months post-Dose 1 and at 24 months post-Dose 1	
2	RSV_flexible revaccination	Participants receiving the first dose (Dose 1) of RSVPreF3 OA investigational vaccine at Day 1 and a revaccination dose at 24 months post-Dose 1	
3	RSV_1dose	Participants receiving a single dose (Dose 1) of RSVPreF3 OA investigational vaccine at Day 1	

Pooled Group label in tables	Groups to be pooled	Pooled definition for footnote	Comment
Total	RSV_annual, RSV_flexible revaccination and RSV_1dose	Participants receiving one dose of RSVPreF3 OA investigational vaccine at Day 1 in all the three groups	Applicable on data reported up to Month 12
Flexible+1dose	RSV_flexible revaccination, and RSV_1dose	Participants receiving one dose of RSVPreF3 OA investigational vaccine at Day 1 in the RSV_flexible revaccination, and RSV_1dose groups	Applicable on data reported at Month 13, Month 18 and Month 24

Table 3Pooled group names and definition for footnote in the TFLs

Table 4Sub-group names and definitions for footnote in the TFLs

Sub-analysis	Subgroup order in tables	Subgroup label in tables	Subgroup definition for footnote

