5.4.3. Additional considerations

5.4.3.1. Mixed effects model

For the GMTs/GMCs calculation based on the mixed effects model mentioned in Section 5.3.1.1, repeated measures analysis of covariance (ANCOVA) model will be fitted including age category (60-69 YOA , 70-79 YOA and \geq 80 YOA,), study group (RSV_annual, RSV_flexible revaccination and RSV_1dose), sex (male and female), visit (Day 31, Months 6, 12, 13, 18, 24, 25, 30, 36), as fixed effects, pre-vaccination log10-transformed titers/concentrations as a covariate and the response variable is the post-vaccination log10-transformed titers/concentrations. The PROC MIXED procedure in SAS® will be used to carry out the ANCOVA.

The following SAS codes will be used:

For the analysis by study group, study group and visit will be included as the fixed effects in the model

```
Analysis by group
PROC MIXED DATA=SERO method=reml empirical;
CLASS subjid group visit ;
MODEL post-vac=pre-vacc group visit visit*group/ noint s cl;
RANDOM intercept/ subject=usubjid g v vcorr type = un;
REPEATED visit/type=unsubject=subjid;
LSMEANS visit*group/ E cl;
ODS OUTPUT LSMEANS=LS;
RUN;
```

For the analysis by age category, age category and visit will be included as the fixed effects in the model. However, this is only applicable at timepoints where the 3 study groups will be pooled. Otherwise for the timepoints where pooling of the 3 groups is not possible, the fixed effects will include study group, age category and visit.

Analysis by age-category

```
PROC MIXED DATA=SERO method=reml empirical ;
CLASS subjid visit agecat ;
MODEL post-vac=pre-vacc agecat visit visit* agecat /noint s cl;
RANDOM intercept/ subject=usubjid g v vcorr type = un;
REPEATED visit/type=un subject=subjid;
LSMEANS visit*agecat/ E cl;
ODS OUTPUT LSMEANS=LS;
RUN;
```

For the analysis by sex, sex and visit will be included as the fixed effects in the model. However, this is only applicable at timepoints where the 3 study groups will be pooled. Otherwise for the timepoints where pooling of the 3 groups is not possible, the fixed effects will include study group, sex and visit.

Analysis by sex

```
PROC MIXED DATA=SERO method=reml empirical;
CLASS subjid visit agecat ;
MODEL post-vac=pre-vacc sex visit visit* sex / noint s cl;
RANDOM intercept/ subject=usubjid g v vcorr type = un;
REPEATED visit/type=un subject=subjid;
LSMEANS visit*sex/ E cl;
ODS OUTPUT LSMEANS=LS;
RUN;
```

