5.4.3.2. Cell-mediated immune response

Within groups evaluation

- The frequency of RSVPreF3 specific-CD4+ T cells will be displayed graphically using boxplots (min, Q1, median, Q3, max), by group and timepoint.
- The RSVPreF3-specific CD4+/ CD8+ T cell frequencies will be obtained by subtracting the background value to the antigen-induced value, and by setting to 1 all values less than or equal to zero for geomean calculation and graphical representation. Frequencies will be expressed as the number of cells per million of CD4+ T cells.
- More specifically, the frequencies of RSVPreF3-specific CD4+/ CD8+ T cells expressing at least 2 activation markers including at least one cytokine [*Freq*²⁺] will be computed as follows:

$$Freq_{Background}^{2+} = \frac{n_{background}^{2+}}{N_{Background}^{CD4}} \quad \text{and} \quad Freq_{Induction}^{2+} = \frac{n_{Induction}^{2+}}{N_{Induction}^{CD4}},$$

And

$$Freq_{Specific}^{2+} = Freq_{Induction}^{2+} - Freq_{Background}^{2+}$$

where

 $n_{Background}^{2+}$ = number of CD4+ T cells expressing at least 2 activation markers including at least one cytokine after stimulation with medium only (background),

 $n_{Induction}^{2+}$ = number of CD4+ T cells expressing at least 2 activation markers including at least one cytokine after stimulation with a pool of peptides covering RSVPreF3 (induction),

 $N_{Back/Ind}^{CD4}$ = Total number of CD4 T cells involved in the assay (background or induction).

For the computation of the fold increase (post- over pre-vaccination) of the frequency of RSVPreF3-specific CD4+ T-cells identified as expressing **at least 2 activation marker(s) including at least one cytokine*** among CD40L, 4-1BB, IL-2, TNF- α , IFN- γ , IL-13, IL-17.the results below the LLOQ of the assay will be replaced by the value of the LLOQ.

* cytokines are IL-2, TNF-α, IFN-γ, IL-13, and IL-17

5.4.3.3. Assessment of long-term persistence of the immune response at Months 18, 24 and 36 after dose 1

The exploratory analysis for modelling the long-term persistence of immune response (humoral and cellular) post dose 1 vaccination will constitute of the following;

- A piece-wise linear mixed model, power law model and modified power law model [David et al, 2009] for repeated measurements (all data available from Day 31, Month 6, 12, 18, 24, 30, 36 post-Dose 1 vaccination, will be used to model over time

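### Single-dose GMTs at Months 30 and 36 gain nothing from RSV_flexible titres to Month 24 or RSV_annual titres to Month 12; a supplementary shared-mean model would sharpen them modestly

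*SAP*

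**What the plan says.** Protocol 9.2 lists among the reasons for the sample size: "Ensure adequate description of the antibody kinetics after a single dose keeping the flexibility to give a revaccination to a part of the participants". Under Protocol 4.2 all groups receive the same first dose; RSV_annual is revaccinated at Months 12 and 24, and for RSV_flexible "A revaccination dose will be given 24 months post-Dose 1". RSV_annual is therefore single-dose to Month 12, RSV_flexible to Month 24 and RSV_1dose to Month 36.

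SAP Amendment 3, 5.4.1, follows this visit by visit. Three groups are pooled to Month 12. The Flexible+1dose pool in Table 3 is "Applicable on data reported at Month 13, Month 18 and Month 24". Later, "From Month 25 up to study end, the analyses will be performed by group". Section 3.1, just above Table 3, says something different: "From Month 13 up to study end, the analyses will be performed by group".

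The model-based GMTs come from 5.4.3.1, with "MODEL post-vac=pre-vacc group visit visit*group/ noint s cl" and the "pre-vaccination log10-transformed titers/concentrations as a covariate". Section 5.4.3.3 adds exploratory decay models for which "all data available from Day 31, Month 6, 12, 18, 24, 30, 36 post-Dose 1 vaccination, will be used to model over time". It names no groups and does not exclude samples drawn after a second dose.

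**The concern.** Persistence to three years after one dose is a stated purpose of the trial (Protocol 2.1 and 4.2), and the Month 30 and 36 titres are secondary endpoints. The tabulated single-dose GMT at these visits uses RSV_1dose only, the smallest single-dose set in the study, and the protocol's precision tables stop at Month 25.

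The mixed model does not make up the difference. The group-by-visit term is saturated, so a RSV_flexible participant's single-dose titres at Months 18 and 24 update the RSV_flexible means and leave the RSV_1dose means alone. Yet those titres estimate the same single-dose mean and correlate with what comes later. At stake is precision. The study is descriptive, so no error rate or power is affected.

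**Working it through.** **1. The plan's own figure.** Half-width = t(0.975, n-1) x SD / sqrt(n). For n = 330 x 0.8^2 = 211 and SD 0.30 to 0.50 this gives 0.041, 0.047, 0.054, 0.061 and 0.068, matching Protocol Table 21 to rounding.

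**2. Same formula, RSV_1dose only.** n = 330 x 0.8^2.5 = 189 at Month 30 and 330 x 0.8^3 = 169 at Month 36. At SD 0.40 the half-widths are 0.057 and 0.061 log10 (upper limit/GM 1.14 and 1.15). Over SD 0.30 to 0.50 the Month 36 half-width is 0.046 to 0.076 (1.11 to 1.19).

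**3. Hand check against the raw mean.** Add 211 RSV_flexible Month 24 values to 169 RSV_1dose participants seen at Months 24 and 36. With rho the Month 24-36 correlation, the width ratio is sqrt(1 - rho^2 x 211/380). The Month 36 interval narrows by 7% at rho 0.5, 15% at 0.7 and 26% at 0.9. This is too generous a comparison, because the planned model already uses Day 1 titres and dropouts' earlier visits.

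**4. Against the planned model.** Generalised least squares with known covariance; visits at Day 1, Day 31 and Months 6 to 36; monotone loss of 20% a year; 330, 330 and 345 participants.
- Planned: one Day 1 mean shared by all groups, separate means by group and visit afterwards.
- Alternative: common means while single-dose, with the same all-group Day 1 mean.

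Assumed correlation between visits d months apart: b + (1-b) x r^(d/6).

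| b, r | rho, M24-M36 | M36 SE (SD units): planned / + RSV_flexible / + both | CI narrower at M30: + RSV_flexible / + both | CI narrower at M36: + RSV_flexible / + both |
|---|---|---|---|---|
| 0.3, 0.7 | 0.64 | 0.0679 / 0.0634 / 0.0630 | 13% / 14% | 7% / 7% |
| 0.5, 0.7 | 0.74 | 0.0619 / 0.0574 / 0.0568 | 13% / 14% | 7% / 8% |
| 0.6, 0.8 | 0.86 | 0.0545 / 0.0497 / 0.0491 | 13% / 15% | 9% / 10% |
| 0.7, 0.8 | 0.89 | 0.0503 / 0.0461 / 0.0456 | 12% / 14% | 8% / 9% |

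**5. Sensitivity to the correlations.**
- Day 1 correlations multiplied by 0.6, both groups added: 16-26% at Month 30 and 9-21% at Month 36.
- First-order autoregressive, 0.5 per 6 months (Month 24-36 correlation 0.25): about 6% and 1%.
- Equal correlation of 0.9 at all lags, both groups added: about 5% at each visit. If only RSV_flexible is added and RSV_annual's Day 1 titres are dropped, the interval becomes about 8% wider than planned, because the planned model uses those titres.

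**6. In practical units.** At SD 0.40, 1.96 x 0.40 x SE turns the planned and + RSV_flexible Month 36 columns into upper limit/GM of 1.13 falling to 1.12 (first row) and 1.095 falling to 1.087 (last row).

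**The case against.** By-group reporting is the right default once the other groups have been revaccinated, and it matches Protocol 9.4.1 and 9.4.4.1. The gain is an option on precision in a descriptive study with no accepted correlate of protection (Protocol 8.1.4), and no stated decision turns on it. That stands; it is why the model should sit beside the by-group GMTs and not replace them.

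Four stronger readings are tempting and not supported:
- **The estimates rest on RSV_1dose alone.** True of the tabulated GMTs. The mixed-model GMTs share baseline slope, Day 1 mean and covariance across groups.
- **The gain is 9-20% at Month 36 from RSV_flexible alone.** That follows for the same four settings if Day 1 is left out of the comparison. The planned model adjusts for Day 1.
- **This is the trial's whole three-year persistence result.** Section 5.4.3.3 also plans persistence models. They are exploratory, impose a decay shape and do not give the endpoint's visit GMTs, but they exist. The mixed model also gives RSV_1dose GMTs at every visit.
- **The gain is free because of randomisation.** It needs no new samples. It does need equal means among attending per-protocol participants of an open-label trial, and missingness at random. The SAP already relies on the first when it pools and on the second in its mixed model. RSV_annual sera come only from the CMI subset, so they are a randomised match only to the roughly 115 CMI-subset participants of RSV_1dose; using them requires adjustment for subset.

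**Conclusion.** The point holds as a modest, inexpensive gain in precision. The plan leaves randomised single-dose titres out of the Month 30 and 36 single-dose means. Against the planned baseline-adjusted model, using them would narrow the 95% CI by roughly 12-15% at Month 30 and 7-10% at Month 36 under the four settings tabulated. Weak Day 1 correlation raises this to about 26% and 21%; a low Month 24-36 correlation cuts the Month 36 gain to about 1%. All these sizes rest on assumed correlations, the protocol's 20% yearly loss, equal means before revaccination and missingness at random.

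Two drafting gaps need correcting whatever the gain. Section 3.1 contradicts Table 3, the opening of Section 5 and 5.4.1 on Months 13, 18 and 24. Section 5.4.3.3, read literally, would admit post-revaccination titres into a single-dose decay model.

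**What to change.** In 5.4.3.1, prespecify a supplementary single-dose model for each assay and keep the by-group GMTs.
- **Data:** only samples drawn before a participant's second dose. Main version: RSV_flexible to Month 24 and RSV_1dose to Month 36. Second version: add RSV_annual to Month 12, adjusted for CMI subset.
- **Model:** common visit means, Day 1 log10 titre as covariate, unstructured covariance. Evaluate the LS means at the same all-group Day 1 mean as the by-group model; otherwise the main version can lose precision.
- **Report:** Month 30 and 36 LS-mean GMTs with 95% CIs beside the by-group values, stating the equal-means and missing-at-random assumptions.

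Also align 3.1 with Table 3, Section 5 and 5.4.1, and state in 5.4.3.3 which groups and visits enter, so that post-revaccination samples are excluded.

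The cost is SAP text and one extra model per assay (two with the RSV_annual version), with no new participants, visits or blood samples.
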